# 11. EVALUATION AND CALCULATION OF VARIABLES

# **11.1** Calculation or derivation of safety variable(s)

All AEs will be collected for each volunteer from the time when informed consent is obtained until the follow-up visit.

# **11.2** Calculation or derivation of pharmacokinetic variables

The PK analysis of ticagrelor and its metabolite AR-C124910XX will be the responsibility of the Pharmacokineticist at . Standard Operating Procedures and Work Instructions will be used as the default methodology if not otherwise specified. Actual sampling times will be used for the computation of PK parameters.

Pharmacokinetic parameters will be derived using standard non-compartmental methods with WinNonlin® Professional Version 5.2, or higher. All PK computations will be performed using WinNonlin® Professional Version 5.2 (or higher) or SAS® Version 9.2 or higher.

Volunteers who withdraw from the study following administration of the investigational product, but prior to study completion, will be included in the PK analysis provided they have evaluable concentrations over the planned collection period. Volunteers with partial data will be evaluated on a case-by-case basis to determine if sufficient data are available for meaningful analysis.

If data permits, the following plasma PK parameters will be calculated for ticagrelor and its metabolite AR-C124910XX for each treatment:

- Observed maximum plasma concentration (Cmax)
- Time of maximum concentration  $(t_{max})$
- Area under plasma concentration-time curve from zero (pre-dose) to the last quantifiable concentration [AUC(0-t)]
- Area under plasma concentration-time curve from zero (pre-dose) to infinity (AUC)
- Apparent terminal half-life  $(t_{1/2})$

Additionally, the following will also be computed:

AR-C124910XX: ticagrelor ratios for Cmax, AUC(0-t), and AUC.

The following PK diagnostic parameters will be calculated for both analytes, as appropriate, and will be listed, but not summarised:

- The time interval ( $t_{1/2}$ , interval) of the log-linear regression to determine  $t_{1/2}$
- Number of data points  $(t_{1/2}, N)$  included in the log-linear regression analysis to determine  $t_{1/2}$  (a minimum of 3 points will be used)
- Regression coefficient (Rsq), a goodness-of-fit statistic for calculation of  $\lambda_z$ . If Rsq is less than 0.800, then  $t_{1/2}$  and related parameters will not be reported
- Percent AUC that is extrapolated (%AUCex). If %AUCex is greater than 20% then AUC will not be reported.

# 12. STATISTICAL METHODS AND SAMPLE SIZE DETERMINATION

#### **12.1** Description of analysis sets

#### 12.1.1 General principles

The analysis of data will be based on different subsets according to the purpose of analysis, ie, for safety and PK. The decision regarding validity of data for each of the analysis sets will be based on a blind review of data.

The as-treated principle will be applied to all evaluations; ie, volunteers who received another treatment than the one assigned in the randomisation list will be analysed as belonging to the actual treatment group and not that assigned by randomisation.

#### 12.1.2 All Subjects

All volunteers who received an enrolment number and at least 1 dose of the investigational product.

#### 12.1.3 Safety analysis set

All volunteers who received at least 1 dose of the investigational product and for whom any post-dose data are available will be included in the safety analysis set. Volunteers will be analysed according to the treatment they actually received. The safety analysis set will be used as the primary analysis set for the reporting of safety data.

#### 12.1.4 Pharmacokinetic analysis set

The PK analysis set will be a subset of the safety analysis set and will include only volunteers who receive at least 1 dose of the investigational product and have at least 1 post-dose plasma concentration measurement at a scheduled time point without important protocol deviations/violations or events thought to significantly affect the PK (eg, volunteer vomited at or before 2 times median  $t_{max}$ ; wrong dose administered; prohibited concomitant medication; etc).

## **12.2** Methods of statistical analyses

#### 12.2.1 General principles

The statistical analyses will be performed using SAS®, Version 9.2 or higher. Standard Operating Procedures and Work Instructions will be used as the default methodology if not otherwise specified. Graphics will be prepared using SAS® Version 9.2 and Sigmaplot® 9.0.

Missing data will result in a reduced sample size for that parameter. No action will be taken to handle missing data.

No adjustment for multiplicity will be made.

A volunteer who withdraws prior to the last planned observation in a study period will be included in the analyses up to the time of discontinuation.

All data will be included in the data listings. Any data excluded from the summaries and statistical analyses will be flagged accordingly

Data will be presented by treatment for the purpose of summarising the safety results. A volunteer who withdraws prior to the last planned observation in a study period will be included in the analyses up to the time of discontinuation.

Tabulations and listings of data for vital signs, clinical laboratory tests, ECGs, and physical examination findings will be presented. All continuous safety data will be summarised across all treatments for the absolute value at each scheduled assessment and for the corresponding change from baseline.

#### Demographic data and baseline data

Demographic data, baseline characteristics, and disposition of volunteers will be summarised for 'All subjects' (Section 12.1.1). Demographic and baseline characteristic data recorded at the screening visit will be listed. Demographic data will include date of birth, age, and gender. Baseline characteristics will be summarised across all volunteers. Volunteer characteristics and baseline data will include smoking status and history and physical examination findings.

Continuous variables will be summarised using descriptive statistics (n, mean, standard deviation [SD], minimum [min], median and maximum [max]) by treatment group. Categorical variables (eg, gender) will be summarised in frequency tables (frequency and proportion of volunteers in analysis set).

In general, descriptive statistics will follow the rounding convention in Global Standard Operating Procedures.

#### Subject identification and disposition

A listing of the enrolment code and the volunteer randomisation number will be produced. This list will also indicate whether the volunteers' data are included in the safety analysis sets. Listings will also be produced which detail why enrolled volunteers who received ticagrelor and AR-C124910XX, the active metabolite of ticagrelor were not randomised and why randomised volunteers withdrew prematurely from the study.

#### 12.2.2 Safety and tolerability

The following safety clinical assessments will be done: AEs, vital signs, physical exams, clinical chemistry and haematology, and ECGs. All safety data (scheduled and unscheduled) will be presented in the data listings.

All safety data (scheduled and unscheduled) will be presented in the data listings. Continuous variables will be summarised using descriptive statistics (n, mean, SD, min, median, max) by treatment at each scheduled time and for the corresponding change from baseline where applicable. Categorical variables will be summarised in frequency tables (frequency and proportion) by treatment group and by scheduled time where applicable. Safety variables (eg, clinical laboratory values and vital signs) will be reported to the same precision as the source data. Derived variables will be reported using similar precision to those from which they were derived (eg, QTc derived from QT interval).

Extra measurements (such as unscheduled or repeat assessments) will not be included in the descriptive. All AEs, ECG outliers, and clinical laboratory outliers that occur following the first administration of the investigational product will be included in the tabulations of AEs and outlier events, including episodes that occur at unscheduled evaluations.

All available data from volunteers in the safety analysis set will be included in the safety analyses. No adjustment or imputation will be utilised for missing values or for volunteers who withdraw prior to completing the study, neither will analyses be restricted to volunteers with complete data.

All AEs will be collected for each volunteer from the time when informed consent is obtained until the follow-up visit. Adverse events that occur before dosing will be reported separately. Adverse events will be summarised by Preferred Term and System Organ Class using Medical Dictionary for Regulatory Activities (MedDRA) vocabulary (Version 12.0 or higher) by treatment and across all treatments, as appropriate. Furthermore, listings of SAEs and AEs that lead to withdrawal will be presented and the number of volunteers who have any AEs, SAEs, AEs that lead to withdrawal, and AEs with severe intensity will be summarised.

For clinical laboratory tests, listings of values for each volunteer will be presented with abnormal or out-of-range values flagged. Clinical laboratory data will be reported in Système International units in the CSR.

#### **Adverse Events**

All AEs will be collected for each volunteer from the time when informed consent is obtained until the follow-up visit. Adverse events that occur before administration of the investigational product will be reported separately.

Adverse events will be summarised by Preferred Term and System Organ Class (SOC) using MedDRA vocabulary (Version 12.0 or higher) by treatment and across all treatments. Furthermore, listings of SAEs and AEs that lead to withdrawal will be made and the number of volunteers who have any AEs, SAEs, AEs that lead to withdrawal, and AEs with severe intensity will be summarised.

All AEs occurring at any time during the study will be listed. All summary tables of AE data will include all AEs starting or worsening after administration of the investigational product. Overall summaries of AEs will be provided at both the volunteer level and the event level, detailing the number of AEs, SAEs, discontinuations due to AEs and other significant AEs by treatment. Adverse events will be summarised by treatment by SOC and preferred term assigned to the event using the MedDRA vocabulary. In volunteer level summaries, a volunteer will only be counted once in each SOC or preferred term. Adverse events will also be summarised by treatment by maximum intensity and by investigator's causality assessment. In addition, separate listings for all SAEs, OAEs, deaths and discontinuations due to AEs will be presented.

Any AEs determined to be of interest or occurring frequently may be summarised separately using the same methodology as described above.

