Dyspnoea was observed in patients with coronary artery disease (CAD) but rarely in healthy subjects. Ticagrelor does not appear to affect respiratory parameters in elderly subjects, patients with asthma or chronic obstructive pulmonary disease, and stable CAD patients.

When ticagrelor was administered orally to healthy subjects for 5 days under controlled conditions of diet, activity, and fluid intake, serum uric acid levels increased approximately by 10%, with no extreme individual elevations, and returned to baseline within 60 hours of discontinuing ticagrelor.

Ticagrelor (single 900 mg dose) had no cardiac ventricular repolarisation effect during the first 24 hours after administration compared with placebo as assessed by QT interval. In the PLATO study, more patients had ventricular pauses >3 seconds with ticagrelor than with clopidogrel, however, there were no adverse clinical consequences associated with this imbalance (including pacemaker insertions) in this population of patients.

For further relevant pre-clinical and clinical data see the current Investigator's Brochure.

In addition, this study requires application of a nasogastric tube and nose bleeding is not an uncommon effect with nasogastric tube insertion, therefore nasogastric tube will be applied by someone with experience. AstraZeneca will immediately notify the Investigator of important safety data that becomes available during the study.

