- b Updating of medical/surgical history to be done on Day -1 of treatment period 1 only.
- c To be performed within 24 hours prior to administration of the investigational product in each treatment period.
- d Complete physical examination at screening and follow-up. Height (centimetres) and weight kilograms) and BMI will be measured at screening only
- e Vital signs will be recorded at screening, pre-dose, 1 hour, 3, 6, 12 and 24 hours post-dose, Day 3 for all treatment periods and follow-up visit
- f Safety laboratory assessments should be analysed and checked before randomisation.
- g In self declared post-menopausal female volunteers only
- h Includes hepatitis B, hepatitis C, and human immunodeficiency virus (HIV) screens.
-  For female volunteers only; urine pregnancy test will be performed at screening, Day -1 (all treatment periods) and at follow-up.
- j Will occur on Day 1 of treatment period 1.
- k Pharmacokinetic blood sampling will be done at pre-dose, 0.5, 1, 2, 3, 4, 6, 8, 10, 12, 16, 24, 36 and 48 hours post-dose for determination of ticagrelor and AR-C124910XX concentrations in plasma.
-  Serious adverse events (SAEs) will be collected from the time of obtaining informed consent through to the follow-up visit. All other AEs will be collected from the time of the first dose on Day 1 (treatment period 1) through to the follow-up visit.
- m Discharge from the study centre will be after the PK sampling at 48 hours post-dose is obtained.
- n According to randomised treatment.

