#### 6.3.3 Recording of adverse events

#### Time period for collection of adverse events

Adverse events will be collected from the time of signature of informed consent throughout the treatment period and including the follow-up period.

All SAEs will be recorded from the time of informed consent.

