#### **Causality collection**

The Investigator will assess causal relationship between the investigational product and each AE, and answer 'yes' or 'no' to the question 'Do you consider that there is a reasonable possibility that the event may have been caused by the investigational product?'

For SAEs causal relationship will also be assessed for other medication and study procedures. Note that for SAEs that could be associated with any study procedure the causal relationship is implied as 'yes'.

A guide to the interpretation of the causality question is found in Appendix B to the CSP.

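### Table 1 contradicts Section 6.3.3 on when non-serious AEs are collected, and the AE summary rule gives nasogastric-tube insertion events no stated place under Treatment C

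*Protocol*

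**What the plan says.** **Collection.** Footnote l of Table 1 (Section 3.1) collects SAEs from consent, but for the rest: "All other AEs will be collected from the time of the first dose on Day 1 (treatment period 1) through to the follow-up visit". Section 6.3.3 says: "Adverse events will be collected from the time of signature of informed consent throughout the treatment period and including the follow-up period". Sections 11.1 and 12.2.2 also start all AEs at consent, Section 6.2.1 records AEs at screening, and the AE-monitoring row of Table 1 is marked at screening and on Day -1.

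**Summaries.** Under Adverse Events in Section 12.2.2: "All summary tables of AE data will include all AEs starting or worsening after administration of the investigational product". Earlier events are covered by "Adverse events that occur before administration of the investigational product will be reported separately" and "All AEs occurring at any time during the study will be listed". The opening part of the same section uses a different anchor: AEs and outliers "that occur following the first administration of the investigational product will be included in the tabulations of AEs and outlier events".

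**Timing and procedure.** Section 5.5.2 sets the time of administration at the last of the water swallowed or injected through the tube. Section 1.4 states that "nose bleeding is not an uncommon effect with nasogastric tube insertion". Section 2.2 makes safety and tolerability of the three ways of giving the drug, the tube included, the secondary objective.

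**Causality.** Every AE gets a yes/no rating against the product. Beyond that, "For SAEs causal relationship will also be assessed for other medication and study procedures".

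**The concern.** Tube insertion is the one procedure that only Treatment C involves, and its acknowledged harm occurs before the dose. A summary rule that starts the clock at dosing therefore tends to miss the event that most distinguishes the tube from the oral routes. The conflict over collection makes this worse. Site staff cannot follow both the footnote and Section 6.3.3, and an event that was never recorded cannot be recovered by any later analysis rule.

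At stake is the by-treatment AE table for the secondary objective. A reader comparing its columns could conclude that the tube is better tolerated than it was, for a drug whose main risk is bleeding.

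**Working it through.** The protocol gives no figure on this point to reproduce. The check compares passages and then counts sequences.

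**1. When collection starts.**

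| Place | Start for non-serious AEs |
|---|---|
| Table 1, footnote l | First dose, period 1 |
| Table 1, AE-monitoring row | Screening |
| Section 6.2.1 | Screening |
| Sections 6.3.3, 11.1, 12.2.2 | Informed consent |

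The footnote stands alone against the rest.

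**2. Where an insertion event falls.** The tube must be in place before the suspension and flush can go through it, and administration is timed at the end of that water. An event that starts at insertion is therefore pre-dose in its own Treatment C period. It enters the summaries as post-dose in that period only if it worsens afterwards.

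**3. Two readings of the summary rule.**
- *Administration means that period's dose.* The insertion event is pre-dose in every period. It is listed and reported separately, but is in no treatment column.
- *Administration means the first dose of the study*, as in the opening part of Section 12.2.2. An insertion event in period 2 or 3 must be tabulated, but no column is named. If the most recent dose decides, the column is A or B, because C is given only once.

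Neither reading states a route into the C column.

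**4. How many volunteers.** Section 5.2.1 gives a Williams design with six sequences in equal ratio. For three treatments these are ABC, ACB, BAC, BCA, CAB and CBA. With 36 volunteers there are 36 / 6 = 6 per sequence.
- C in period 1 (CAB, CBA): 2 × 6 = 12
- C directly after A (ACB, BAC): 2 × 6 = 12
- C directly after B (ABC, BCA): 2 × 6 = 12

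So insertion precedes any dose for 12 of 36 and follows an oral dose for 24 of 36. With 30 volunteers spread evenly over the sequences, the counts are 10 and 20.

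**5. Size.** Let p be the rate, per insertion, of events that start before the end of administration and do not worsen after it. The protocol does not give p; 5% to 30% is an assumption. Counting only these events, correct placement gives C = p and A = B = 0, a contrast of p.
- *Excluded only:* C = 0 and A = B = 0. The contrast is 0, so the error is p.
- *Last-dose attribution:* C = 0 and A = B = 12p / 36 = p/3. The contrast is −p/3, so the error is p + p/3 = 4p/3.

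| Assumed p | Events, 36p | Before any dose, 12p | Added to each of A and B, p/3 (points) | Error if excluded, p (points) | Error under last-dose attribution, 4p/3 (points) |
|---|---|---|---|---|---|
| 5% | 1.8 | 0.6 | 1.7 | 5 | 6.7 |
| 10% | 3.6 | 1.2 | 3.3 | 10 | 13.3 |
| 20% | 7.2 | 2.4 | 6.7 | 20 | 26.7 |
| 30% | 10.8 | 3.6 | 10.0 | 30 | 40.0 |

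Both errors favour Treatment C. The events in the third column are also the ones that go uncollected, if non-serious, when footnote l is followed.

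**The case against.** A reader might infer that the protocol books tube nosebleeds to the oral treatments. It does not say so. The only mention of the last administered dose is in the rule for AEs with missing start times, and Section 12.2.2 has no rule for assigning AEs to treatments across periods. The separate reporting of pre-dose AEs can be read per period, in which case nothing moves to A or B. A statistical analysis plan could also settle attribution. All of this stands, so the 4/3 figure is an upper case and not a prediction.

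A reader might also infer that these events are hidden. Once collected, they are listed and reported separately, and Section 12.2.2 allows frequent events or events of interest to be summarised on their own. Events are lost outright only if footnote l is followed, and then only non-serious ones before the first dose.

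Nor does it follow that a tube bleed cannot be told from a drug bleed. Each AE carries a start date and time and a causality rating against the product, and AEs are summarised by that rating. In periods 2 and 3 insertion comes about 7 days after the previous dose. Against the longest half-life in Section 3.2 (20 hours), that is 168 / 20 = 8.4 half-lives.

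Finally, volunteers with frequent or significant nosebleeds are excluded, experienced staff place the tube, and safety is summarised descriptively without a planned treatment contrast. These points lower the likely size and the severity. They do not remove the contradiction over collection, and they do not give insertion events a stated place under Treatment C.

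**Conclusion.** The point holds on two counts. First, footnote l contradicts Sections 6.2.1, 6.3.3, 11.1 and 12.2.2 and Table 1's own AE-monitoring row. If the footnote is followed, non-serious insertion events go unrecorded for the one third of volunteers (12 of 36) who receive C first. Second, an insertion event that does not worsen after dosing has no stated route into the Treatment C summaries. C misses such events by their full rate if they are only excluded, and the contrast with oral dosing is off by up to 4/3 of the rate if they are assigned to the last dose.

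The counts assume 36 volunteers spread equally over six sequences; the event rate is not in the protocol. The documents do not support the stronger claims that transfer to A or B is prescribed or that the events are concealed. Only the descriptive secondary safety objective is affected; the primary pharmacokinetic analysis is not. Severity: should-fix. The collection conflict needs settling before enrolment, because uncollected data cannot be recovered.

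**What to change.** 1. Change footnote l of Table 1 to agree with Section 6.3.3, so that all AEs, serious or not, are collected from consent.
2. In Section 12.2.2, state that AEs with onset from the start of tube insertion in a Treatment C period are summarised under Treatment C, or in a by-treatment table of procedure-related events, and not under the previous period's treatment. Use one meaning of administration throughout the section.
3. Optionally, collect the study-procedure causality item for non-serious AEs as well as SAEs.

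The first two are wording changes. The third adds one eCRF field. None needs extra visits or volunteers.

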#### Laboratory data

Safety laboratory data consists of clinical chemistry, haematology and urinalysis. These data will be summarised by treatment group. For clinical laboratory tests, listings of values for each volunteer will be presented with abnormal or out-of-range values flagged. Clinical laboratory data will be reported in Système International units in the CSR.

Absolute values will be compared to the project extended reference range and classified as low (below range), normal (within range or on limits of range) and high (above range). All values classified as high or low will be flagged on the listings. The qualitative urinalysis data will be summarised at each time point by treatment group.

Local laboratory reference ranges will be used for the primary interpretation of laboratory data by physicians. The project reference ranges will be based on the AstraZeneca reference ranges where they exist; otherwise project reference ranges agreed by the Patient Safety Physician and the study physician will be used. Both the project and the local laboratory ranges will be listed.

Numerical laboratory data will be summarised using standard summary statistics for each treatment group at each visit. Discrete laboratory data will be summarised showing the number of volunteers at each level of measurement at each visit by treatment group. Summaries of the number of volunteers falling outside the reference ranges at each time point will also be provided by treatment group. Separate listings of only those values falling outside these reference ranges will also be produced.

